## EXPERIMENTAL DESIGN SCHEMA

\*Participants treated at the tolerable dose from Safety Lead-in will be included in the Phase 2 portion if they are evaluable for response.

^An early stopping rule for futility is based on the response rate in the first 7 patients treated at the tolerable dose.

†Day 2 dose should not be administered until the 24 hours post-dose lab results are reviewed by the investigator.

**PROTOCOL SYNOPSIS****Protocol Title**

A Phase 2 Study of Venetoclax and Romidepsin with Safety Lead-in for Treatment of Relapsed/Refractory Mature T-cell Lymphomas

**Study Detail**

Population/Indication(s):	Peripheral T-cell Lymphoma (PTCL)
Phase:	Safety Lead-in/ Phase 2
Sample Size:	Safety Lead-in: 6 evaluable Phase 2: 18 evaluable (Safety Lead-in patients included)
Estimated Accrual Duration:	24 months
Estimated Study Duration	6 years
Participant Duration:	48 months
Participating Sites:	
 
• City of Hope Duarte, CA
 
• University of Nebraska
 

Study Agents:	Venetoclax, Romidepsin
Sponsor:	City of Hope
Industry Partner:	AbbVie, Celgene
Industry Partner Protocol #:	11354

**Rationale for this Study**

Peripheral T cell lymphomas (PTCL) arise from post thymic lymphocytes, representing non-Hodgkin lymphoma (NHL) in the western populations. Based on immunophenotyping, molecular, clinical and pathologic features, there are about 22 different subtypes of PTCL that are broadly classified into nodal, extranodal, leukemic variant and cutaneous T cell lymphomas (CTCL) based on the site of origin of the disease. Approximately 5,000 new cases of PTCL are diagnosed annually in the US. Most PTCL cases have a dismal prognosis with a 5 year survival of less than 30% with the exception of ALK+ ALCL.

The Bcl-2 family proteins are important regulators of the intrinsic apoptosis pathway. Bcl-2 over-expression is a major contributor to the pathogenesis of some types of lymphoid malignancies and has been extensively studied in B cell lymphomas, including CLL and DLBCL. In studies of T-cell lymphoma at City of Hope, Bcl-2 has been found to be expressed in 52-76% of cases of PTCL and 25% of CTCL. So far there is no published data regarding the use of Bcl-2 inhibitors in the treatment of peripheral T cell lymphomas and cutaneous T cell lymphomas.

Venetoclax (also known as ABT-199) is a novel, orally available, small molecule Bcl-2 family protein inhibitor that binds with high affinity to Bcl-2 and with lower affinity to other Bcl-2 family proteins such as Bcl-xL and Bcl-w. There is currently clinical experience with venetoclax in CLL/small lymphocytic leukemia and B-cell NHL. In the Phase 1 study of venetoclax in diffuse large B-cell lymphoma and follicular lymphoma the overall response rate was 15% and 34% with a median duration of response of 3.3 months and 10 months, respectively. In diffuse large B-cell lymphoma, there is an ongoing trial evaluating the combination of venetoclax with rituximab or obinutuzumab plus CHOP (NCT02055820). We hypothesize that interference of BCL2 will lead to antitumor activity in mature T-cell lymphomas.

## Objectives

### Primary Objectives

#### *Safety Lead-in:*

- To assess the safety and tolerability of the combination of venetoclax with romidepsin, including the dose ramp-up, in adults with relapsed or refractory mature T-cell lymphoma.

#### *Phase 2:*

- To estimate the efficacy as measured by the overall response rate (ORR) of venetoclax with romidepsin in patients with relapsed or refractory mature T-cell lymphoma.

### Phase 2 Secondary Objectives

- To evaluate the complete response rate, duration of response, time to response, overall survival and progression free survival associated with venetoclax and romidepsin in relapsed/refractory mature T-cell lymphoma.
- To further characterize the safety and toxicities of venetoclax and romidepsin combination in relapsed/refractory mature T-cell lymphoma.

### Exploratory Objective

- BCL2 protein expression in baseline treatment tumor samples and correlation with response
- To determine changes in Bcl-2 gene expression in pre- and post-treatment tumor samples of mature T- cell lymphoma

## Study Design

This is an open-label multi-site Phase 2 study with a Safety Lead-in to test the safety and efficacy of venetoclax with romidepsin for the treatment mature T-cell lymphoma.

During the safety-lead in, 6 evaluable participants will be enrolled using a 3+3 design. A Simon 2-stage optimal design will be utilized for the Phase 2 portion of the trial. Participants enrolled during the Safety Lead-in will be included in the Phase 2 portion of the study if they are evaluable for response. In the absence of study holds to accrual for toxicity or for futility, accrual will continue until 18 evaluable participants are treated.

PTCL patients will be treated with up to 26 cycles with venetoclax and romidepsin. Treatment cycles will be 28-days.

Participants will continue with treatment until disease progression, unacceptable toxicity or completion of 26 cycles of protocol therapy, whichever comes first.

## Evaluation Criteria and Endpoints

### Safety

Toxicity will be recorded using the NCI CTCAE v 5.0. During the first 2 cycles, all grades of toxicity will be collected. After cycle 2, only the highest grade of any toxicity will be collected for each cycle during protocol treatment and for the period of safety follow-up after end of treatment.

### Unacceptable toxicity for Safety Lead-in

Unacceptable toxicity will be defined as one of the following AEs that is at least possibly related to either study drug within the **first 2 cycles** of protocol therapy:

- *Hematologic*
  - Grade 3 or 4 neutropenia lasting > 7 days (despite the use of growth factor support)
  - Grade 4 thrombocytopenia associated with bleeding requiring transfusion
  - Grade 4 anemia not associated with lymphoma
- *Non-hematologic*
  - Clinical TLS (per Howard criteria)
  - Grade 4 metabolic laboratory abnormalities that do not resolve within 3 days to ≤ Grade 2 with supportive measures
  - Any other ≥ Grade 3 toxicity that does not resolve to ≤ Grade 1 or baseline within 7 days with the exception of:
  - Grade 3 asymptomatic laboratory abnormalities, including lipase or amylase, that are not clinically relevant, not requiring hospitalization or delay of treatment
  - Grade 3 nausea, vomiting, or fatigue controlled with supportive measures
  - Vitiligo

#### Response

Lugano Criteria 2014

#### Clinical Outcome Endpoints

Endpoint	Definition
Overall response rate (ORR)	Proportion of patients achieving CR or PR
Complete response (CR) rate	Proportion of patients achieving CR
Time to response	Date of initiation of protocol treatment to date when criteria for response (PR or CR) is first met
Duration of response (DOR)	Date when criteria for response (CR or PR) is first met until date criteria for PD or relapse is first met
Progression free survival (PFS)	Date of initiation of protocol treatment to date criteria for PD is first met or death as a result of any cause
Overall survival (OS)	Date of initiation of protocol treatment to date of death from any cause

#### Statistical Considerations

##### Safety Lead-in

Up to 6 patients may be enrolled under a “3+3” design at the proposed dose (maximum dose of 800 mg/day with a 1-week dose ramp up schedule). Unacceptable toxicities will be evaluated during the first 2 cycles of therapy. This will ensure monitoring of participants during the ramp-up period (Cycle 1, Days 1-8) and while participants are on steady-state dose (Cycle 1 Days 8-28, Cycle 2). Initially up to 3 patients can be enrolled and treated. After 3 patients are treated and evaluated for unacceptable toxicities, if 0/1 out of 3 patients experience unacceptable toxicities during the first 2 cycles, up to 3 additional patients will be enrolled and treated to bring the total number of patients treated to 6. If ≤1/6 patients experience unacceptable toxicities during the first 2 cycles, the proposed treatment dose/schedule will be considered tolerable and be used for the subsequent Phase 2 response evaluation. If ≥2/3 (after the initial 3) or ≥2/6 (after the total 6 in 2 cohorts) patients experience unacceptable toxicities during the first 2 cycles, the accrual will be suspended and the study will be amended.

##### Phase 2

The primary endpoint for Phase 2 is ORR after 2 cycles of treatment. The response evaluation will be based on a Simon’s Two-Stage Optimal design to distinguish a promising 30% response rate (alternative hypothesis) from a disappointing rate (null hypothesis) of 10%, at a one-sided type I error of 10% and a power of 80%. In the first stage, 7 evaluable subjects will be accrued. If there is 0 response among the 7, the study accrual will be suspended. If there are 1 or more responses among the 7, the study will remain open to accrue a total of 18 evaluable patients. Observing 4 or more responses among 18 evaluable patients will

reject the null hypothesis and indicate the response rate being promising in this study setting. Observing 3 or fewer responses among 18 evaluable patients will fail to reject the null hypothesis and will not establish efficacy of the treatment.

#### Stopping rules for Tumor Lysis Syndrome (TLS)

The study will implement accrual stopping rules for both clinical TLS and laboratory TLS. When a stopping rule is triggered, the study PMT will review and assess the safety of the trial and submit a report to the COH DSMC. The COH DSMC will review for approval any decision to continue or permanently suspend accrual to the trial.

- Clinical TLS Stopping Rule
- Study accrual will be suspended when the first incidence of clinical TLS is reported.
- Laboratory TLS Stopping Rule

The incidence of laboratory TLS will be monitored with 12% being the benchmark based on IB. Operationally, the study accrual will be suspended if:

- 1 patient experiences laboratory TLS when there have been  $\leq 5$  patients treated
- 2 patients experience laboratory TLS when there have been  $\leq 14$  patients treated
- 3 patients experience laboratory TLS regardless of the number of patients treated

The rule is derived based on a <50% probability of the rule being triggered when the true laboratory TLS incidence is  $\leq 12\%$ .

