### **12.2 Accrual and Expected Duration of Trial**

The expected sample size for the Phase 2 response evaluation is 18 patients evaluable for response (assuming the response evaluation passes the first stage). Patients enrolled during the Safety Lead-in of the romidepsin/venetoclax combination will be included in the Phase 2 response evaluation if they are evaluable for response which requires a response evaluation after 2 cycles. We expect that all patient enrolled during safety lead-in will have a response evaluation after 2 cycles. Therefore, the total sample size for the study including the Safety Lead-in is expected to be 18 evaluable patients. Assuming approximately 10% of the patients need to be replaced for safety lead-in or Phase 2 evaluation, the maximum sample size for evaluating the combination of venetoclax and romidepsin is 20 patients.

The 6 patients enrolled on the previous versions of protocols with single agent venetoclax will be analyzed separately and excluded from the main analyses which evaluate the combination of venetoclax and romidepsin. Therefore, the maximum sample size of the study will be 26 accounting for these 6 prior enrollments.

City of Hope saw ~160 PTCL patients per year, with ~30 new patients per year (mix of newly diagnosed and relapsed or refractory). This will be a multicenter study with 3 total sites. We expect a total accrual of 1-2 patients per month across all sites. Therefore, accrual is expected to be completed in 24 months.

Participant duration is planned for 4 years which includes maximum time for treatment (24 months) and expected post-treatment follow-up (24 months). The estimated total study duration will be 6 years, with 2 years of accrual and approximately 4 years of treatment and follow-up for the last patient.

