### 12.4.2 Laboratory TLS Stopping Rule

The incidence of laboratory TLS will be monitored with 12% being the benchmark based on IB. Operationally, the study accrual will be suspended if:

- 1 patient experiences laboratory TLS when there have been  $\leq 5$  patients treated
- 2 patients experience laboratory TLS when there have been  $\leq 14$  patients treated
- 3 patients experience laboratory TLS regardless of the number of patients treated

The rule is derived based on a  $<50\%$  probability of the rule being triggered when the true laboratory TLS incidence is  $\leq 12\%$ .

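### At the 12% benchmark the laboratory TLS stopping rule triggers with probability 64–66%, not below 50% as stated

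*Combined protocol and SAP*

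**What the plan says.** The synopsis (stopping rules for TLS) and Section 12.4.2 give the same rule. The reference rate is set by "The incidence of laboratory TLS will be monitored with 12% being the benchmark based on IB". Accrual is suspended at any of three boundaries:

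- "1 patient experiences laboratory TLS when there have been" 5 or fewer treated
- "2 patients experience laboratory TLS when there have been" 14 or fewer treated
- "3 patients experience laboratory TLS regardless of the number of patients treated"

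Both places then describe the rule's performance: "The rule is derived based on a <50% probability of the rule being triggered when the true laboratory TLS incidence is" 12% or lower. This is the only operating characteristic given for the laboratory TLS rule. The plan does not say whether the probability is cumulative over the trial or applies to each boundary separately.

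Section 12.2 supplies the horizon: "the total sample size for the study including the Safety Lead-in is expected to be 18 evaluable patients", and with replacements "the maximum sample size for evaluating the combination of venetoclax and romidepsin is 20 patients". The 6 earlier single-agent patients are analysed separately.

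A trigger leads to an assessment by the protocol management team and a report to the DSMC, which reviews any decision to continue or to suspend accrual permanently.

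**The concern.** The first boundary alone uses up almost all of a 50% allowance: the chance of at least one event in 5 patients at 12% is 47.2%. Two further boundaries then apply to the patients who follow, so the total can hardly stay below 50%.

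The sentence tells the protocol management team, the DSMC and the IRB how to read a suspension. If the rule fires less than half the time at the benchmark rate, a trigger points towards an excess. If it fires about two times in three at that rate, a trigger is weaker evidence, and at least one accrual hold should be expected in planning the 24-month accrual.

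**Working it through.** **Inputs.** Incidence p = 0.12, and the boundaries 1 in ≤5, 2 in ≤14 and 3 at any time (synopsis and Section 12.4.2). Number treated N = 18 expected and 20 at most (Section 12.2). Patients are taken as independent.

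**Step 1: can the stated figure be reproduced one boundary at a time?** Binomial tails at p = 0.12:

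| Boundary | Probability |
|---|---|
| ≥1 of 5: 1 − 0.88⁵ | 47.2% |
| ≥2 of 14: 1 − 0.88¹⁴ − 14(0.12)(0.88¹³) = 1 − 0.1670 − 0.3188 | **51.4%** |
| ≥3 of 18 | 36.9% |
| ≥3 of 20 | 43.7% |

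The boundaries look as if they were built this way. Five is the largest number for which P(≥1) stays below 50% (6 patients give 53.6%). The second boundary nevertheless misses: 13 patients would give 47.4%, and 14 give 51.4%.

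**Step 2: the whole rule.** The event count never falls, so no trigger occurs by patient N only if there are 0 events in patients 1–5, at most 1 in patients 6–14, and at most 2 in total by N. With m = N − 14 and cⱼ the binomial probability of j events in m patients:

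P(no trigger) = 0.88⁵ × [A(c₀ + c₁ + c₂) + B(c₀ + c₁)]

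Here 0.88⁵ = 0.5277, A = 0.88⁹ = 0.3165, and B = 9(0.12)(0.88⁸) = 0.3884.

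- N = 18 (m = 4): c₀ + c₁ + c₂ = 0.9937 and c₀ + c₁ = 0.9268. P(no trigger) = 0.5277 × (0.3145 + 0.3600) = 0.3559, so P(trigger) = **64.4%**.
- N = 20 (m = 6): the sums are 0.9739 and 0.8444. P(no trigger) = 0.5277 × (0.3082 + 0.3280) = 0.3357, so P(trigger) = **66.4%**.

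A patient-by-patient recursion gives the same values, and a simulation of 400,000 trials gives 64.4% for N = 18. Cumulatively, the probability is 47.2% by patient 5, 48.0% by patient 7, 51.1% by patient 9 and 62.8% by patient 14.

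**Step 3: other true rates.** Probability of at least one trigger:

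| True incidence | 18 treated | 20 treated |
|---|---|---|
| 5% | 28.5% | 29.0% |
| 8% | 45.4% | 46.7% |
| 12% | 64.4% | 66.4% |
| 25% | 94.4% | 95.7% |

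The probability reaches 50% at an incidence of about 8.9% (N = 18) or 8.6% (N = 20).

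**Step 4: other readings of the boundaries, at 12%.**

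| Reading | 18 treated | 20 treated |
|---|---|---|
| Strict inequalities (<5, <14) | 60.6% | 63.2% |
| Second boundary ending at 13 | 62.9% | 65.3% |
| First boundary dropped | 53.8% | 56.8% |

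None falls below 50%.

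**The case against.** Four points can be made for the plan.

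**The basis is unstated, and a per-boundary derivation is plausible.** Two of the three boundaries meet the criterion on their own, and the third misses by only 1.4 points. If each boundary is instead credited only with the triggers it adds, the second contributes 15.6 points (29.5% among trials that pass patient 5) and the third 1.6 to 3.6 points. Every step is then below 50%. But the sentence speaks of the rule as a single thing, which most naturally means any of the three boundaries, and a per-step contribution is not the probability that the rule is triggered.

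**Not every trial treats 18 to 20 patients.** The Simon design stops at 0 responses in 7. The probability of that is 0.9⁷ = 47.8% at a 10% response rate and 0.7⁷ = 8.2% at 30%. Suppose TLS and response are independent and a futility stop leaves 7 treated. The trigger probability at 12% is then 0.478 × 48.0% + 0.522 × 64.4% = 56.6% (57.6% with a maximum of 20) at a 10% response rate, and 63.1% (64.9%) at 30%. The 64–66% figure is thus conditional on full accrual and should be labelled so. The stated property still fails.

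**The consequence is confined to rates near the benchmark.** This is correct: below about 8.6% the rule does trigger less than half the time. The plan, however, claims the property all the way up to 12%.

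**The error is cautious.** The boundaries are explicit and identical in both places, a trigger brings review and not automatic closure, and no endpoint, sample size or efficacy analysis changes. That supports leaving the boundaries alone. It does not support leaving a false probability beside them.

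**Conclusion.** The stated property is wrong as written. At a true incidence of 12% the rule triggers with probability 64.4% (18 treated) or 66.4% (20 treated), about 14 to 16 points above the stated ceiling. Weighting for the futility stop leaves it at 56.6% to 64.9%. Read one boundary at a time, the 2-in-14 boundary still exceeds 50%, though only by 1.4 points.

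The main figures assume independent patients, all 18 to 20 treated, and the 6 single-agent patients not counted. They do not allow for suspension during the safety lead-in or under the separate clinical TLS rule.

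This needs correcting because the sentence is the only performance figure given for a safety decision rule.

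**What to change.** In the synopsis and in Section 12.4.2, replace the sentence with the actual operating characteristics. State that they are cumulative and conditional on 18 to 20 patients treated: at least one suspension has probability about 28–29% at 5% true incidence, 64–66% at 12%, and 94–96% at 25%.

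If a probability below 50% at 12% is a property the sponsor requires, the boundaries must be re-derived jointly over all looks. Shortening the second boundary to 13 patients would bring it below 50% on its own but would leave the cumulative probability at 62.9% to 65.3%.

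Without that requirement the cost is one sentence in two places. The stated figure becomes less favourable, and the existing boundaries and the conduct of the trial do not change.

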#### **Abbreviated Eligibility Criteria**

##### Main Inclusion Criteria

- Adult relapsed/refractory PTCL (WHO criteria 2016) excluding CTCL. Transformed mycosis fungoides is allowed.
- ECOG  $\leq 2$
- Failed at least 2 prior systemic therapies
- Measurable disease (CT/MRI/PET-CT). At least one measurable lesion (Lugano 2014)
- ANC  $\geq 1,000/\text{mm}^3$  \* (unless documented bone marrow involvement by lymphoma)
- Platelets  $\geq 30,000/\text{mm}^3$  \* (unless documented bone marrow involvement by lymphoma)
- Total bilirubin  $\leq 1.5 \times \text{ULN}$  (except Gilbert's Syndrome or documented hepatic involvement by lymphoma)
- ALT and AST  $\leq 3 \times \text{ULN}$  ( $\leq 5 \times \text{ULN}$  if hepatic involvement by lymphoma)
- Creatinine clearance of  $\geq 50 \text{ mL/min}$

\* Platelet transfusions/ growth factor not permitted within 7 days of assessment unless cytopenia is secondary to disease involvement

[figure not shown]
##### Main Exclusion Criteria

- Bcl2 inhibitors
- Any systemic therapy, including monoclonal antibody within 28 days or 5 half-lives (whichever is shorter) of initiating protocol therapy
- Radiation and/or surgery (except lymph node or other diagnostic biopsies) within 14 days prior to Day 1 of protocol therapy
- Strong or moderate CYP3A inhibitors within 7 days prior to Day 1 of protocol therapy
- Strong or moderate CYP3A inducers within 7 days prior to Day 1 of protocol therapy
- P-gp inhibitors within 7 days prior to Day 1 of protocol therapy.
- Narrow therapeutic index P-gp substrates within 7 days prior to Day 1 of protocol therapy.
- Short course systemic corticosteroids for disease control, improvement of performance status or non-cancer indication within 7 days prior to Day 1 of protocol therapy. Stable ongoing corticosteroid use (i.e. at least 30 days) up to an equivalent dose of 20 mg of prednisone is permissible.

- Patients with known cardiac abnormalities such as:
  - Congenital long QT syndrome
  - QTc (Corrected QT interval on ECG) interval >480 milliseconds
  - Any cardiac arrhythmia requiring anti-arrhythmic medication.
- Patients with a history of sustained ventricular tachycardia (VT), ventricular fibrillation (VF), Torsade de Pointes, or cardiac arrest, unless currently addressed with an automatic implantable cardioverter defibrillator (AICD).

### Investigational Product Dosage and Administration

- All participants (safety lead-in and Phase 2) will ramp-up daily over the first week of Cycle 1 to the maximum venetoclax dose. From Cycle 1 Days 8-28 and Cycle 2+ Days 1-28, participants will continue at the maximum dose.
- Patients will be monitored for TLS on an outpatient basis for the first 8 days of treatment.

### Clinical Observations and Tests to be Performed

- Medical history and physical exam
- Safety assessments (CBCs with differential, comprehensive chemistry panel, EKG and coagulation)
- Post-dose TLS monitoring during Cycle 1
- CT/ MRI/ PET-CT scans
- Correlative tumor tissue

**ABBREVIATIONS**

Abbreviation	Meaning
AE	Adverse Event
AESI	Adverse Event of Special Interest
BSA	Body Surface Area
BUN	Blood Urea Nitrogen
CBC	Complete Blood Count
CFR	Code of Federal Regulations
COH	City of Hope
CR	Complete Response
CRC	Clinical Research Coordinator
CRF	Case Report Form
CT	Computed Tomography
CTCAE	Common Terminology Criteria for Adverse Events
CTCL	Cutaneous T-Cell Lymphoma
CTEP	Cancer Therapy Evaluation Program
Diff	Differential
DSMC	Data & Safety Monitoring Committee
ECP	Extracorporeal Photopheresis
FDA	Food and Drug Administration
FDG	[  F]fluorodeoxyglucose
GCP	Good Clinical Practice
HIV	Human Immunodeficiency Virus
HDAC	Histone deacetylase
IB	Investigator's Brochure
IDS	Investigational Drug Services
IND	Investigational New Drug
INR	International Normalized Ratio
IRB	Institutional Review Board
IV	Intravenous
MRI	Magnetic Resonance Imaging
NCCN	National Comprehensive Cancer Network
NCI	National Cancer Institute
OIDRA	Office of IND Development and Regulatory Affairs
ORR	Overall Response Rate
PD	Progressive Disease
PET	Positron Emission Tomography
PI	Principal Investigator
PLT	Platelets
PMT	Protocol Management Team
PR	Partial Response
PT	Prothrombin
PTCL	Peripheral T-cell Lymphoma
SAE	Serious Adverse Event
SD	Stable disease
SOC	Standard of Care
SOP	Standard Operating Procedure
TNMB	Tumor, Node, Metastasis, Blood
Tx	Protocol Therapy
TBSA	Total Body Surface Area
TLS	Tumor Lysis Syndrome
ULN	Upper Limit of Normal

